## 5.5 Guidelines for Discontinuation of Participant from Study

Participants who are no longer on treatment but are still followed on the study can be terminated from the study for the following reasons:

- Completion of protocol-defined follow-up period
- Uncontrolled intercurrent illness unrelated to cancer that prevents continuing study follow-up
- Noncompliance with protocol-required evaluations
- The participant requests to be discontinued from the study, i.e., withdrawal of consent
- The sponsor, investigator, or regulatory agency terminates the study
- Death

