**MGC018 Monotherapy Dosing Schedule (Q3W) (Module A)**

**Note: Imaging for tumor assessments will be every 9 weeks (63 days) during the Cohort Expansion Phase for Module A.**

**Figure 7**

**MGC018 and MGA012 Combination Dosing Schedule (Q3W) (Module B)**

For both the Dose Escalation Phase of Module A and Module B and the Cohort Expansion Phase of Module B, tumor assessments will occur at Day 42 of each cycle, for the first 4 cycles, and every other cycle thereafter. For the Cohort Expansion Phase of Module A, the tumor assessments will occur every 9 weeks (63 days). For Module A, the DLT evaluation period will be 21 days in duration; for Module B, the DLT evaluation period will be 42 days in duration (see [Section 4.1.1](#) below for more details). Participants who complete a given cycle, remain clinically stable, do not experience a DLT or other unacceptable toxicity, and do not otherwise meet the criteria for permanent treatment discontinuation may be eligible for additional treatment with MGC018 alone or in combination with MGA012 for up to a total of 18 cycles (approximately 2 years). For participants with a dose delay > 21 days, the total number of cycles may be < 18 cycles and the time on MGC018 will be no more than 2 years.

Following the last dose of study drug, all participants in Module A and Module B Cohort Expansion Phases will be followed every 3 months (90 days) for survival during a 2-year Survival Follow-up Period, until criteria are met for study discontinuation. Participants in Module A Dose Escalation Phase will be followed similarly for survival status until approval of Amendment 3, at which point they will be discontinued from follow up.

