## 9.17 Post-Treatment Follow-up Visit

The Post-Treatment Follow-up period includes the following:

- Survival follow-up for participants in the Cohort Expansion Phase of Module A or Module B: approximately a 2-year period for each participant following the last dose of MGC018; this period runs until the last participant in the study completes his/her survival follow-up period. Participants in Module A Dose Escalation will be followed for survival status until approval of Amendment 3, at which point they will be discontinued from follow up.
- During this time, participants will be followed via clinic visit, telephone, paper mail, or other electronic contact at 3-month (90 days) intervals for follow-up of OS.
- For mCRPC participants, serum testosterone and PSA will be collected approximately every 12 weeks during the follow-up period until disease progression, start of another cancer therapy, or the study cutoff date, whichever comes first.
- Response status: information regarding response status and/or the occurrence of disease progression may be collected every 3 months (90 days) on all participants who discontinued from study treatment due to reasons other than PD, if they have not initiated any other cancer-directed therapy. Tumor response results (e.g., CT imaging results) may be entered in the electronic data capture (EDC) system if available per standard of care procedures to document the date of progression.

Post-Treatment Follow-up is performed until the end of study for each participant. Survival follow-up will be discontinued for participants enrolled in Module A Dose Escalation Phase after the approval of Amendment 3.

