#### 11.1.2 Survival Assessments

Participants who are discontinued from study treatment in the Cohort Expansion Phase of Module A or Module B will be followed for survival status every 3 months (90 days) for a 2-year survival follow-up period following the last dose of MGC018 alone (Module A) or in combination with MGA012 (Module B), or until the event of death, they withdraw consent, or are lost to follow-up (see [Section 9.17](#)). Survival follow-up will be discontinued for participants enrolled in Module A Dose Escalation after the approval of Amendment 3.

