6.7.2.3 Analyses of Overall Survival

The Kaplan-Meier method will be applied to estimate OS curve, median OS, and OS rates at 6 and 12 months. For patients who are not known to be dead at the time of data cut-off for OS analysis, the OS will be censored at the time they are last known to be alive. The method of Brookmeyer and Crowley ([1](#)) will be used to construct 95% CI for median OS. The 95% CIs for OS rate at 6 and 12 months will be calculated by normal approximation after log(-log) transformation. OS will be analyzed by tumor type when sample size warrants.

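### Protocol 5.5 lets non-cancer illness or noncompliance end survival follow-up while 11.1.2 does not; illness exits that precede death can bias the exploratory OS estimate upward

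*Protocol*

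**What the plan says.** Protocol 5.5 opens: "Participants who are no longer on treatment but are still followed on the study can be terminated from the study for the following reasons". Among the reasons it lists are "Uncontrolled intercurrent illness unrelated to cancer that prevents continuing study follow-up" and "Noncompliance with protocol-required evaluations".

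Several other places let a 5.5 exit close survival follow-up:

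- Section 4.1 follows survival for 2 years "until criteria are met for study discontinuation". The Survival Assessments part of the synopsis and SAP 3.1 say the same.
- Section 4.5.2 defines a participant's end of study as loss to follow-up or any reason in 5.5.
- Section 9.17 closes with: "Post-Treatment Follow-up is performed until the end of study for each participant".

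Section 11.1.2 is different. It follows survival for 2 years "or until the event of death, they withdraw consent, or are lost to follow-up". Neither illness nor noncompliance is on that list.

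Contact for survival is light. Under 9.17, "participants will be followed via clinic visit, telephone, paper mail, or other electronic contact at 3-month (90 days) intervals for follow-up of OS". Declaring a participant lost to follow-up under 5.3 takes at least three documented attempts and then a certified letter.

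OS runs from first dose to death from any cause (Protocol 14.6.3, SAP 5.1.2). For anyone not known to be dead, "the OS will be censored at the time they are last known to be alive" (SAP 6.7.2.3). OS is an exploratory objective (Protocol 3.3, SAP 2.3).

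**The concern.** A site that follows 5.5 may stop seeking vital status in a case where 11.1.2 tells it to continue. The two 5.5 reasons require no contact attempt, although a telephone call or letter would be enough to learn whether the participant is alive.

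For the illness reason the statistical issue is specific. OS counts non-cancer deaths. A participant who leaves because of a serious non-cancer illness is likely to be at higher risk of death than those who stay, yet Kaplan-Meier treats a censored participant as having the same later risk as those still followed. If such exits come before deaths, the OS curve sits too high. Deaths after the exit are not collected, so no later analysis recovers them. The SAP plans no sensitivity analysis for OS, and its optional one for PFS (6.7.2.1) can only reclassify events that were observed.

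**Working it through.** **Inputs.** The documents give no OS median, no rate of 5.5 exits and no interval from exit to death, so there is no OS figure in the plan to reproduce. What follows from the documents is the event (all-cause death), the censoring rule, the Kaplan-Meier OS rates at 6 and 12 months, and the expansion cohort size of up to 16, with up to 4 more. Assumed here: exponential survival with median *m* of 9, 12 or 18 months, and a fraction *f* of deaths (5%, 10% or 20%) replaced by censoring shortly before death.

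**Step 1: limiting bias.** If a fraction *f* of deaths is replaced by censoring just before the event, the observed hazard is (1 − f) times the true one. Kaplan-Meier then estimates S(t)^(1−f), with S(12) = 0.5^(12/m). For m = 12 and f = 10%, this is 0.5^0.9 = 53.6% in place of 50.0%.

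| Assumed median | True 12-month OS | f = 5% | f = 10% | f = 20% |
|---|---|---|---|---|
| 9 months | 39.7% | 41.6% (+1.9) | 43.5% (+3.8) | 47.7% (+8.0) |
| 12 months | 50.0% | 51.8% (+1.8) | 53.6% (+3.6) | 57.4% (+7.4) |
| 18 months | 63.0% | 64.5% (+1.5) | 66.0% (+3.0) | 69.1% (+6.1) |

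The median becomes m/(1 − f). For m = 12 that is 12.6, 13.3 and 15.0 months.

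**Step 2: simulation check.** Kaplan-Meier was run on 400,000 simulated survival times per scenario, with censoring on average 1 or 3 months before death. The rise in 12-month OS was:

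| Mean interval from exit to death | f = 5% | f = 10% | f = 20% |
|---|---|---|---|
| 1 month | 1.5-1.7 points | 2.9-3.5 points | 5.9-7.4 points |
| 3 months | 1.4-1.5 points | 2.7-3.0 points | 5.5-6.5 points |

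These are slightly below the limit and in the same direction.

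**Step 3: exits unrelated to risk.** With censoring times drawn independently of death, the bias was zero to within 0.1 point. A noncompliance exit therefore biases OS only if it is linked to the risk of death.

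**Step 4: one cohort.** With m = 12, 0.5^(24/12) = 25% are alive at 24 months, so 75% have died. In a cohort of 16, one lost death is f = 1/(16 × 0.75) = 8.3%, and 12-month OS moves from 50% to 0.5^0.917 = 53.0%. The standard error, ignoring other censoring, is √(0.5 × 0.5/16) = 12.5 points. With 20 participants the figures are 52.4% and 11.2 points.

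**Step 5: PFS and rPFS.** Section 5.5 applies only off treatment. Progression is a reason to stop treatment (5.4), and those participants are already events. Starting another anticancer therapy censors in any case, as does a death directly after two or more missed scheduled assessments (Protocol Table 11, SAP Table 2). This leaves participants who stopped without progression and started no new therapy. The documents do not allow their number to be estimated.

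**The case against.** The strongest case on the other side is that this is an untidy list and not a defect in the analysis.

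- Section 5.5 is headed as guidelines and is permissive. Its illness reason applies only where the illness prevents follow-up, and if a call or letter suffices the condition should rarely be met. This stands in part: the clause does not say which follow-up is meant, and for mCRPC follow-up also includes PSA and testosterone samples about every 12 weeks (9.17), which illness could prevent without preventing a call.
- Most of the protocol agrees with 5.5, so 11.1.2 is the odd one out. This is correct as a reading. It also means that the rule which loses deaths is the one most sections support.
- Expansion participants need a life expectancy of at least 24 weeks, and significant cardiac and pulmonary disease is excluded, so fatal non-cancer illness may be uncommon. This stands, and makes the 20% scenario an upper illustration.
- OS is exploratory, has no comparator or decision rule, and may be left out of the study report. SAP 6.3.1 tabulates end-of-study status and duration of follow-up, so early exits should be visible. This stands too, although it does not recover the deaths.

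A reader might infer that reported OS will be too high, or that noncompliance exits add to the bias in the same way as illness exits. The documents support neither: no exit rate is given, and Step 3 shows no bias where exit is unrelated to risk. Section 9.16 does recognise that participants with progression may elect not to return to the site, so independence is not assured either.

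**Conclusion.** The conflict between 5.5 (with 4.1, 4.5.2, 9.17 and the synopsis) and 11.1.2 is real. Illness exits that precede death would be informative censoring and would push Kaplan-Meier OS upward; noncompliance exits would do so only if related to the risk of death.

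The size is conditional. With assumed medians of 9 to 18 months, losing 5%, 10% or 20% of deaths raises 12-month OS by about 1.5-2, 3-4 or 6-8 points. One lost death in a cohort of 16 moves it about 3 points against a standard error of about 12.5. Pooling cohorts would shrink the standard error but not the bias. All medians and fractions are assumptions.

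It might also be inferred that rPFS, a secondary objective whose 6-month rate underlies the mCRPC sample size, is compromised in general. The documents do not support that, because only participants who stopped without progression or new therapy are exposed. The point is worth correcting because the change is cheap and deaths left uncollected may be unrecoverable after database lock, not because a large error has been shown.

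**What to change.** Align Protocol 5.5, 4.1, 4.5.2, 9.17, 11.1.2 and the synopsis, with the matching sentence in SAP 3.1. State that illness or noncompliance ends scheduled evaluations but not vital-status contact by the telephone, mail or electronic means already in 9.17. That contact should stop only for death, withdrawn consent, loss to follow-up as determined under 5.3, completion of the follow-up period, or termination of the study. The existing Amendment 3 stop for Module A Dose Escalation is unaffected.

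In SAP 6.7.2.3, add a count of OS censorings by reason, with 5.5 illness and noncompliance exits shown separately. The end-of-study CRF page (4.5.2) already records the status needed.

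The cost is a wording change, one small table and a few extra remote contacts.

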## **6 STUDY TREATMENTS**

### **6.1 Description of Treatments**

For Module A, MGC018 will be administered on Days 1 and 22 of each 42-day cycle. For Module B, MGC018 will be administered on Days 1 and 22 of each 42-day cycle. In addition, for Module B, MGA012 will be administered on Day 22 of Cycle 1 and on Days 1 and 22 of every 42-day cycle thereafter. Each cycle is 42 days.

MGC018 will be administered as an IV infusion over 60 minutes. MGA012 will be administered by IV infusion over 60 minutes. On days when the MGC018 and MGA012 are to be administered on the same day (Module B only), MGA012 should be given first, followed immediately thereafter by MGC018. MGC018 and MGA012 will be administered as separate IV infusions.

### **6.2 Method of Assigning Participants to Treatment Groups**

Participants will be assigned sequentially to the dose escalation cohorts and cohort expansion cohorts as specified in [Section 4.1.1](#) and [Section 4.1.2](#), respectively. Participants in the Cohort Expansion Phase will receive doses of MGC018, alone (Module A) or in combination with MGA012 (Module B), at the MTD (or MAD if no MTD is defined) based on results from the Dose Escalation Phase of the respective modules. A predetermined number of participants will then be enrolled in each cohort.

### **6.3 Blinding**

This is an open-label study.

### **6.4 Emergency Unblinding**

Not applicable. This is an open-label study.

### **6.5 Study Drug and Supplies**

#### **6.5.1 MGC018**

[REDACTED]

MGC018 must be diluted with sterile 0.9% Sodium Chloride Injection, USP (normal saline), prior to administration. MGC018 will be administered by IV infusion over 60 minutes. MGC018 must not be administered as an IV push or bolus.

## **6.5.2            MGA012**

MGA012 must be diluted with sterile 0.9% Sodium Chloride Injection, USP (normal saline), prior to administration. MGA012 will be administered by IV infusion over 60 minutes. MGA012 must not be administered as an IV push or bolus.

**Table 8** **MGA012 Drug Product Composition**

## **6.6 Study Infusion Preparation**

### **6.6.1 General Guidelines and Precautions**

Under no circumstances is the investigator allowed to release these clinical supplies for use by another physician not named on Form FDA 1572 or equivalent form or to administer study drug to a participant who is not enrolled in this study. Study drug must be dispensed at an institution specified on Form FDA 1572 or equivalent form.

#### **6.6.1.1 MGC018 (Module A and B)**

The calculated dose of MGC018 will be administered based on the participant's actual weight at Cycle 1, Day 1 (or up to 24 hours prior to Cycle 1, Day 1). In the cohort expansion phase, the MGC018 dose will be capped for participants with a body weight  $\geq 100$  kg. Body weight will be measured at Screening and Days 1 and 22 of each cycle. Significant ( $\geq 10\%$ ) change in BW from baseline should prompt recalculation of dose using the most recent body weight. Refer to the pharmacy manual for further instructions on allowable parameters for dose rounding.

MGC018 should not be administered as an IV push or bolus. All doses of MGC018 will be diluted in normal saline and administered as an IV infusion over 60 minutes with a commercially available infusion pump or syringe pump. All infusion pumps must be calibrated in accordance with the institutional standards, policies, and procedures to ensure consistent, accurate delivery of MGC018.

Infusion or allergic reactions may occur with the infusion of monoclonal antibodies and other protein-based therapeutics. Precautions for anaphylaxis should be observed during administration. Supportive measures may include, but are not limited to, epinephrine, antihistamines, corticosteroids, IV fluids, vasopressors, oxygen, bronchodilators, diphenhydramine, and acetaminophen. Please refer to **Section 7.1** for specific guidelines

regarding the management of infusion reactions. Supportive care measures consistent with optimal participant care will be provided throughout the study according to institutional standards.

On days when the MGC018 and MGA012 are to be administered on the same day (Module B only), MGA012 should be given first, followed immediately thereafter by MGC018.

Note: Participants should remain in the infusion center for 4 hours after the completion of administration of the first dose of **MGC018 alone (Module A, Day 1 of Cycle 1)**. For **Module B**, participants should remain in the infusion center for 4 hours after the completion of administration of the first dose of **MGC018 alone** (Day 1 Cycle 1) and 4 hours after the completion of the first dose of combined administration of **MGC018 and MGA012** (Day 22, Cycle 1).

#### **6.6.1.2 MGA012 (Module B only)**

MGA012 should not be administered as an IV push or bolus. All doses of MGA012 will be diluted in normal saline and administered as an IV infusion over 60 minutes with a commercially available infusion pump or syringe pump. All infusion pumps must be calibrated in accordance with the institutional standards, policies, and procedures to ensure consistent, accurate delivery of MGA012. Refer to the pharmacy manual for instructions on infusion preparation.

MGA012 dose will be administered as per **Table 4**.

Infusion or allergic reactions may occur with the infusion of monoclonal antibodies and other protein-based therapeutics. Precautions for anaphylaxis should be observed during MGA012 administration. Supportive measures may include, but are not limited to, epinephrine, antihistamines, corticosteroids, IV fluids, vasopressors, oxygen, bronchodilators, diphenhydramine, and acetaminophen. Please refer to **Section 7.1** for specific guidelines regarding the management of infusion reactions. Supportive care measures consistent with optimal participant care will be provided throughout the study according to institutional standards.

#### **6.6.2 Study Drug Preparation and Administration**

Visually inspect parenteral drug products for particulate matter and discoloration prior to administration. Return the vial if the solution is cloudy, there is pronounced discoloration (solution may have pale-yellow color), or there is foreign particulate matter.

Instructions on the thawing and preparation of the study drugs (MGC018 and MGA012) for IV infusion are detailed in the pharmacy manual.

Do not mix the study drugs with, or administer as an infusion with, other medicinal products.

### **6.6.2.1 MGC018**

All doses of MGC018 must be diluted in sterile 0.9% Sodium Chloride Injection, USP (normal saline) prior to dose administration. MGC018 diluted in normal saline must be within the concentration range of 0.1 mg/mL to 6.0 mg/mL for syringe pump administration and 0.5 mg/mL to 2.9 mg/mL for infusion pump administration. Administer the diluted dosing solution over 60 minutes through an IV line with a commercially available infusion pump or syringe pump. Up to 10 additional minutes of infusion time (i.e. up to a total infusion time of 70 minutes) is permitted to allow for flushing the line. A sterile, non-pyrogenic, low protein binding PES 0.2  $\mu$ m in-line filter administration set should be used for IV administration of MGC018. Do not administer as an IV push or bolus.

Because there is no preservative and drug loss may occur over time. The administration of study drug should begin immediately after preparation, but no later than 4 hours at room temperature after preparation. Alternatively, the dose-prepared IV bag or syringe may be stored for up to 24 hours at 2° to 8°C. If the dose solution is stored at 2° to 8°C, it should be removed from the refrigerator at least 30 to 60 minutes prior to administration, to allow solution to reach room temperature. If there is a delay in administration of study drug such that the drug will not be administered according to the above parameters, the medical monitor must be notified immediately, and instructions on how to proceed will be provided.

### **6.6.2.2 MGA012**

All doses of MGA012 must be diluted to a concentration range of 0.3 mg/mL to 12.0 mg/mL in sterile 0.9% Sodium Chloride Injection, USP (normal saline). Administer the diluted dosing solution over 60 minutes through an IV line with a commercially available infusion pump. A sterile, non-pyrogenic, low protein binding PES 0.2  $\mu$ m in-line filter administration set must be used for IV administration of MGA012. MGA012 should not be administered as an IV push or bolus.

The administration of study drug should begin immediately after preparation. The administration should be no later than 4 hours and study drug kept at room temperature after preparation. Alternatively, the dose-prepared IV bag may be stored for up to 24 hours at 2° to 8°C. If the dose solution is stored at 2° to 8°C, it should be removed from the refrigerator at least 30 to 60 minutes prior to administration, to allow solution to reach room temperature. If there is a delay in administration of study drug such that the drug will not be administered according to the above parameters, the medical monitor must be notified immediately, and instructions on how to proceed will be provided.

### **6.6.3 Combination Therapy**

When MGC018 and MGA012 are to be administered on the same day (Module B only), MGA012 should be given first, followed immediately thereafter by MGC018.

After MGA012 infusion, the IV line should be cleared with normal saline infusion given at the same rate as the MGA012 infusion.

**Do not manually push normal saline after MGA012 or MGC018 infusion.**

## **6.7 Treatment Compliance**

The study drug will be administered by healthcare professionals under the supervision of the investigator or designee. Records of dose calculation, administration, and dosing regimen will be accurately maintained by site staff. The monitor will review dose calculation, administration, and regimen as well as medication accountability during study site visits and at the completion of the study.

